This project involves obtaining peripheral blood mononuclear cells (PBMCs) and colorectal tissue samples from study participants to measure adenylate kinase 2 (AK2) and muscle-type creatine kinase (CKM) enzyme levels in an “older adult” group (65-80) when compared to a “younger adult” group (18-50). Both AK2 and CKM has been demonstrated to be vital enzymes in converting the prodrug tenofovir (TFV) into its active form, tenofovir diphosphate (TFV-DP).¹⁻⁴ However, no study has yet investigated the effect of aging on AK2 or CKM in colorectal tissues relevant to HIV infection and prevention. This study will investigate the AK2 and CKM variability in individuals from the younger and older age groups in preparation for a follow-up study investigating how the pharmacokinetics (PK) of tenofovir (TFV) vary with altering levels of cellular enzymes in different age populations. A finding of clinically significant differences in the activity of AK2 or CKM, may indicate the need for dose adjustment of TFV for HIV treatment or prevention depending upon age to either reduce toxicity or enhance efficacy.

In this study, individuals who are interested in participating will be screened for eligibility. If eligible, participants will return for a single study visit. At the study visit, blood will be drawn and colorectal tissue will be obtained via flexible sigmoidoscopy. Participants can participate in an optional PK sub-study if they are already taking a tenofovir (TFV)-based regimen for prevention or are willing to take a daily TFV-based regimen for 7 days prior to the flexible sigmoidoscopy. Subsequently, AK2 and CKM will be analyzed in PBMCs and colorectal tissue using mass spectrometry.

II. INTRODUCTION

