Previous studies have found that age has an effect on CKM expression, post-translational modifications, and activity in multiple tissues.¹¹⁻¹⁶ Thus, it is hypothesized that expression levels and post translational modifications of AK2 and CKM may differ depending upon age, therefore, altering the amount of active TFV-DP and increasing variability of protection. Therefore, it is imperative to investigate expression and post translational modifications of AK2 and CKM in colorectal tissue and PBMCs from various age populations to see if these cellular enzymes change with increasing age.

III. RATIONALE

While PrEP has been shown to be highly effective in reducing the risk of HIV infection, despite adherence to PrEP, some individuals become infected with HIV. To gain an understanding of CKM phosphorylation activity and examine whether CKM might also contribute to variability of TFV-DP activation in colonic CD4+ cells in the presence of HIV infection, we will also measure levels of CKM and TFV-DP in colonic CD4+ T cells of younger and older individuals infected with HIV taking tenofovir-based HIV treatment, as well as those taking tenofovir-based PrEP who are not infected with HIV.

This study is designed to investigate the intracellular AK2 and CKM enzymes in both colorectal tissue and PBMCs in a younger and older adult population. It is hypothesized that age alters expression and post translational modifications and expression of AK2 and CKM in colorectal tissue and PBMCs causing variability in TFV-DP levels in individuals taking tenofovir-based medications.

To test this hypothesis, colorectal biopsies and PBMCs will be collected to assess for changes in AK2 and CKM levels using mass spectrometry and changes in enzymatic activity to phosphorylate TFV from the following populations:

Cohort A: 10 younger (age 18-50) and 10 older (age 65-80) adults who are not infected with HIV and not taking tenofovir-based PrEP ("Control Cohort").

Cohort B: 10 younger (age 18-50) and 10 older (age 65-80) adults who are not infected with HIV, but are taking a TFV-based regimen (either on daily TFV- based PrEP or agree to take a daily TFV-based regimen 7 days prior to procedure). ("PrEP Cohort")

Cohort C: 10 younger (age 18-50) and 10 older (age 65-80) adults who are infected with HIV, taking a TFV-based regimen. ("ARV Cohort")

Study Objectives:

Objective	Endpoint

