1. Determine if levels and activity of AK2 and CKM in colorectal tissue differ between (a) younger adults (age range 18-50 years), and older adults (age range 65-80) or	
 • Proteomics will be used to measure intracellular protein levels and modification status of kinases that phosphorylate TFV. • In individuals taking a TFV-containing regimen, colorectal tissue TFV-DP will be measured at steady-state.

(b) between HIV negative and HIV positive persons.
	
 In individuals not taking a TFV-based regimen, in vitro incubation of TFV with colorectal tissue biopsies will be performed to measure TFV activation as a function of age.

2. Determine if levels and activity of AK2 and CKM in PBMCs differ between:
 
(a) younger adults, defined as 18-50 years of age, and older adults, defined as 65-80 years of age or
 
(b) HIV negative and HIV positive persons..
	
 Proteomics will be used to measure intracellular protein levels and modification status of kinases that phosphorylate TFV. In individuals not taking a TFV-based regimen, in vitro incubations of TFV with PBMCs will be performed to measure TFV activation as a function of age. In individuals taking a TFV-containing regimen, colorectal tissue TFV-DP will be measured at steady-state.

IV. STUDY DESIGN

Overview

The design of the study will be a two-visit study, including a screening visit (Visit 1) and a sampling visit (Visit 2). During the screening visit, the individual will be assessed for eligibility. For participants scheduled for sigmoidoscopy or colonoscopy for a medical indication, the screening visit may be conducted by phone prior to the procedure. If eligible, the participant will return for the study visit ≤ 42 days following the screening visit. During the study visit, approximately 100 mL of blood will be drawn for PBMC isolation. Following the blood draw, participants will undergo endoscopic evaluation in which 10 colorectal biopsy samples will be obtained between 10-20 cm from the anal verge. Thirty adults from each age population (younger and older) will be enrolled for this study. Three cohorts (each including young and old groups) will be defined by TFV administration and HIV status.

Study Population

Three cohorts of participants will be recruited, with 10 younger and 10 older in each cohort.

Cohort A: Healthy Volunteers, not taking TFV based PrEP (Control Cohort)

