Incidental Findings: Significant clinical findings may be discovered during study procedures, which may warrant referral for medical care and further testing. If significant clinical findings are discovered during the procedure, study subjects will be referred to the proper Johns Hopkins Division for additional evaluation and treatment as necessary.

Social Risk: Although the study site will make every effort to protect participant's privacy and confidentiality, it is possible that involvement in the study could become known to others, and that social harms may result (i.e., subjects could become known as HIV-infected or at "high risk" for HIV infection) and, consequently, be treated unfairly or discriminated against by families, friends and/or communities.

Loss of confidentiality: Although every effort will be made to protect the privacy and confidentiality of all participants, it is possible that their involvement in the study could become known to others. All guidelines for the protection of Personal Health Identifiers will be followed.

Benefits

There are no direct benefits to subjects who participate in this study. However, there may be personal satisfaction in the knowledge that they are aiding in important medical research, and that the knowledge obtained from this study will advance the field of HIV prevention. Participants will be reimbursed for their time and inconvenience.

The risks to individual participants are outweighed by potential benefits to the scientific community and to society – namely, contribution to our microbicide knowledge-bank.

IX. STATISTICAL ANALYSIS

To compare protein levels between the younger adult and older adult groups, protein abundances will be averaged within age groups. Differences in protein levels will be determined by unpaired two-tailed t test using the Benjamini-Hochberg correction for multiple comparisons, with significant differences being defined as having an adjusted p-value of <0.05. Based on our previous studies of TFV phosphorylation we estimate ~80% power to detect a 1.5-fold difference between study groups using our measured outcomes and >95% power to detect a 1.75-fold difference between study groups at our sample size.

X. CONFIDENTIALITY

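### Does Section IX leave the activity outcomes (TFV-DP and in vitro TFV activation) without an analysis that their power claim needs?

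*Combined protocol and SAP*

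**What the plan says.** Section IX is the whole statistical plan. It opens with protein: "To compare protein levels between the younger adult and older adult groups, protein abundances will be averaged within age groups". The test follows: "Differences in protein levels will be determined by unpaired two-tailed t test using the Benjamini-Hochberg correction for multiple comparisons", with significance at an adjusted p below 0.05. It closes with power: "Based on our previous studies of TFV phosphorylation we estimate ~80% power to detect a 1.5-fold difference between study groups using our measured outcomes", and more than 95% for a 1.75-fold difference. It gives no SD, scale or group size.

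Activity appears elsewhere. Section III plans to assess "changes in AK2 and CKM levels using mass spectrometry and changes in enzymatic activity to phosphorylate TFV". In the Study Objectives table, Objective 1 begins "Determine if levels and activity of AK2 and CKM in colorectal tissue differ between", and Objective 2 asks the same of PBMCs. Each objective has an age comparison (a) and an HIV comparison (b). For participants on a TFV regimen, "colorectal tissue TFV-DP will be measured at steady-state". For those not on one, tissue biopsies are incubated with TFV, and likewise "in vitro incubations of TFV with PBMCs will be performed to measure TFV activation as a function of age". Section IV sets 10 younger and 10 older adults in each of three cohorts, 30 per age group overall.

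**The concern.** The power claim comes from one kind of outcome and the only stated test is for another. Nothing in the document gives a test, a scale, a rule for combining Cohorts B and C, or a multiplicity rule for TFV-DP or in vitro activation. The opening summary ties the practical message to activity: "A finding of clinically significant differences in the activity of AK2 or CKM, may indicate the need for dose adjustment of TFV". If the cohorts and the error control for that message were chosen after the data were seen, the choice could decide the answer. An uncorrected set of activity tests would also carry a raised false-positive rate.

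**Working it through.** **1. Who contributes to each activity outcome**

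| Outcome | Measured in | Cohorts | Age comparison |
|---|---|---|---|
| In vitro activation, tissue | not on TFV | A | 10 v 10 |
| In vitro activation, PBMCs | not on TFV | A | 10 v 10 |
| TFV-DP, colorectal tissue | on TFV | B and C | 20 v 20 together, or 10 v 10 in each |

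The populations are fixed by the objectives table and the cohort definitions. For in vitro activation nothing is left to choose about cohorts. For TFV-DP only the handling of B and C is open.

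**2. The plan's power figures**

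Inputs: 80% at 1.5-fold and more than 95% at 1.75-fold (Section IX); n = 10, 20 or 30 per group (Section IV). The SD is not given, so it is solved for and is an assumption. Work on the log scale with a two-sided t test at 0.05, where δ = ln(fold) and the noncentrality is λ = δ / (σ√(2/n)). ln 1.5 = 0.405 and ln 1.75 = 0.560.

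- n = 10: σ = 0.306 gives λ = 0.405 / (0.306 × 0.447) = 2.96 against a critical t of 2.10, power 80%. At 1.75-fold it is 97%.
- n = 20: σ = 0.446 gives λ = 2.88 against 2.02, power 80%. At 1.75-fold it is 97%.
- n = 30: σ = 0.551 gives λ = 2.85 against 2.00, power 80%. At 1.75-fold it is 97%.

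The pair is coherent at every possible group size. The raw scale gives 96% (constant CV) or 99% (common SD) at 1.75-fold. The figures cannot be tied to one test, but nothing shows them to be wrong.

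**3. What the choice for B and C does**

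Power for a true 1.5-fold age difference, unadjusted:

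| Power pair read as | Assumed log SD | TFV-DP, B and C together (20 v 20) | One cohort (10 v 10) |
|---|---|---|---|
| 10 v 10 | 0.306 | 98% | 80% |
| 20 v 20 | 0.446 | 80% | 49% |
| 30 v 30 | 0.551 | 62% | 34% |

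The last column also applies to in vitro activation in Cohort A.

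Simulation (300,000 trials, normal log values, 10 per age-by-cohort cell): if TFV-DP also differed 2-fold between B and C (an assumption), a plain pooled t test would fall from 98% to about 85% at SD 0.306, and from 80% to about 62% at SD 0.446. A model with age group and cohort stays at 98% and 80%, and with no B-C difference it matches the pooled t test. So including cohort is the safe default.

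**4. False positives**

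With no true age effect, the pooled test, B alone and C alone each reject in about 5% of trials. At least one of the three rejects in about 12%. Across uncorrected activity tests (activation in tissue and in PBMCs, TFV-DP by age, TFV-DP in B v C), independence gives 1 − 0.95⁴ = 18.5%, or 1 − 0.95⁵ = 22.6% if TFV-DP by age is tested separately in B and C. Correlation between the two activation tests of up to 0.8 lowers these to 17% and 21%.

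These rates describe an analyst who counts any success and corrects nothing. With the plan's own Benjamini-Hochberg rule applied to the same tests, the chance of any false positive when no effect is real is at most 5%, for independent or positively dependent tests.

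**5. What that correction costs**

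For a 10 v 10 test at log SD 0.306 in a family of four, the strictest step is 0.05 / 4 = 0.0125, where 80% becomes 58%. That is the floor. Simulating the full procedure with four independent tests gives about 59% if one effect is real, 67% if two, 72% if three and 77% if all four. Section III expects related changes in both enzymes and in TFV-DP, so the upper part of that range is the relevant one.

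**The case for a change.** The best case for a change is that the study does not present itself as purely descriptive. It claims about 80% power, sets a significance threshold, and links activity to possible dose adjustment. A t test carried over to activity still does not say how B and C combine, and at the assumed log SDs of 0.306 and 0.446 the pooled and B-only conclusions differ in 19% and 36% of trials. One paragraph written before analysis would settle it.

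The factual part stands: that text is absent, and writing it would be good practice. Three things limit its force. First, the closing sentence of Section IX speaks of study groups and measured outcomes in general, directly after the t test; reading that test as meant for every outcome is natural. Second, the disagreement rates compare a 20 v 20 analysis with one that discards half the data, which few analysts would put forward as the main result. Third, the study is described as preparation for a follow-up pharmacokinetic study, and a difference in activity only may point to dose adjustment.

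Nor could such a paragraph do all that is hoped of it. In vitro activation cannot address HIV status, because everyone in Cohort C takes TFV. Under the PBMC objective the only TFV-DP endpoint listed is in colorectal tissue. Section III also mentions TFV-DP in colonic CD4+ T cells, which the test counts above leave out. These are questions about the endpoint table, not about the missing test.

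**Conclusion.** No change to the plan follows. Section IX is silent on the activity outcomes, but no stated rule or figure is shown to give a wrong result, and an analyst would fill the gap sensibly: log in vitro activation by age in Cohort A with the same t test, log TFV-DP by age in B and C together with cohort as a factor, and the same correction across these tests. That route keeps the error rate for TFV-DP by age at 5%. Its cohort term also gives a B v C comparison in tissue.

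The 12% and 17-23% rates need no SD but assume a selective, uncorrected analyst. The power figures (98%, 80% or 62% for TFV-DP in B and C together; 80%, 49% or 34% for Cohort A activation) rest on log SDs solved from the plan's own 80%. They show what is unknown about the power claim, not that the claim is false. The 58% is a worst case.

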APPENDIX I: SCHEDULE OF EVENTS

	Screening Visit	Sampling Visit
Visit Day	< -42	1
Visit #	1	2
ADMINISTRATIVE		
Informed consent	X	
Assessment of Eligibility	X	
HIV/STI Risk Reduction Counseling	X	
Dispense and provide directions for enema ²	X	
Dispense TFV to TFV-naïve participants ³		
CLINICAL		
History/Concomitant meds	X	
Physical Exam, Vital signs, height, weight ¹	X	
Oral TFV-based regimen dosing and virtual DOT ⁶	Day -7 to -1	
SAFETY LABS⁶		
Blood CBC w/ diff, AST, ALT, BUN, Creatinine ²	X	
Blood HIV testing ⁴	X	
Blood syphilis screening ⁵	X	
Rectal swab GC/CT NAT	X	X ⁶
Blood HBsAg ⁶	X	
SPECIMEN COLLECTION		
Blood PBMC		X
Rectal biopsy		X
Blood for TFV ⁶		X

¹After the screening visit, physical exam is symptom-directed; vital signs consist of heart rate and blood pressure only.

²For participants not undergoing a concurrent endoscopy procedure.

³ For PrEP cohort only in participants not already taking PrEP.

⁴See Appendix II: HIV Testing Algorithm. Will not be completed for those with known HIV infection.

⁵Syphilis Chemiluminescence assay (with confirmatory RPR; FTA-ABS performed on RPR negative samples)

⁶For participants in PrEP or ARV Cohort taking TFV-based regimen for 7 days prior to procedure.

⁷With the exception of rectal GC/CT screening, safety labs will not be obtained in participants undergoing screening colonoscopy. In those individuals, rectal GC/CT screening can be performed concurrently with Visit #2.
